## SYNOPSIS

---

**TITLE:** A Phase 2, Randomized, Double-Blind, Placebo-Controlled, Parallel-Group Study to Evaluate the Efficacy and Safety of FX006 in Patients With Glenohumeral Osteoarthritis or Shoulder Adhesive Capsulitis

---

**PROTOCOL NUMBER:** FX006-2018-016

---

**INVESTIGATIONAL PRODUCT:** FX006

---

**PHASE:** 2

---

**INDICATIONS:** Shoulder pain due to glenohumeral osteoarthritis (OA) and shoulder pain due to adhesive capsulitis (AC)

---

### **OBJECTIVES:**

The primary objective of this study is to assess the efficacy of FX006 on pain following an intra-articular (IA) injection in patients with glenohumeral OA or shoulder AC.

The secondary objectives of this study are to assess the efficacy of FX006 on pain, disability, function, and global impression of change in patients with glenohumeral OA or shoulder AC, and to assess the safety of FX006 in patients with glenohumeral OA or shoulder AC.

The exploratory objectives of this study are to assess additional measures of pain, disability, function, QOL, rescue medication consumption, and proportion of responders at varying timepoints over the course of the study.

---

### **POPULATIONS:**

The populations for this study are males or females, 35 to 80 years of age, inclusive, with painful symptoms associated with OA of the index glenohumeral joint for  $\geq 3$  months prior to the Screening Visit and X-ray confirmation of Grade 2 or 3 OA based on the Samilson-Prieto classification system; and male or females, 35 to 80 years of age, inclusive, with pain associated with shoulder AC of the index joint for  $\geq 1$  month but  $\leq 6$  months prior to the Screening Visit, more than 20% (25% if dominant shoulder is the index shoulder) loss of passive range of the rotation arc (external and internal rotation) of glenohumeral movement, measured with the patient in supine or sitting position and the shoulder elevated to 45 degrees, compared with the contralateral shoulder, and no X-ray evidence of OA.

---

### **STUDY DESIGN AND DURATION:**

This is a Phase 2, multicenter, randomized, double-blind, placebo-controlled, parallel-group study in separate cohorts of patients with a documented history of either glenohumeral OA or shoulder AC. Glenohumeral OA and shoulder AC patients will be randomized to 1 of 2 treatment groups within their shoulder condition in a 1:1 ratio to receive a single IA injection of either 32 mg FX006 or placebo (saline) to the index shoulder with a 24-week Treatment Evaluation Period. Glenohumeral OA patients will be stratified by Baseline average daily shoulder pain with

---

---

movement score according to the following classifications: 5.0 to <7.0 or  $\geq 7.0$  to 9.0 (0 to 10 numeric rating scale [NRS]). Shoulder AC patients will be stratified by Baseline average daily shoulder pain with movement score according to the following classifications: 5.0 to <7.0 or  $\geq 7.0$  to 9.0 (0 to 10 NRS), and by pain duration since onset at Screening (1 to 3 months, inclusive, or >3 to  $\leq 6$  months). A Home Exercise Program will be implemented 3 days following injection for shoulder AC patients.

---

#### **DOSAGE FORMS AND ROUTE OF ADMINISTRATION:**

FX006 is an extended-release formulation of triamcinolone acetonide in 75:25 poly (lactic-co-glycolic acid) microspheres. FX006 will be supplied as a sterile, white to off-white powder in a single unit dose 5 mL vial and reconstituted in 5 mL of a diluent containing an isotonic, sterile aqueous solution of sodium chloride (NaCl; 0.9% weight by weight [w/w]) carboxymethylcellulose sodium (0.5% w/w), and polysorbate-80 (0.1% w/w) to form a suspension prior to IA injection. The placebo is sterile normal saline (NaCl). FX006 or placebo will be administered as a 5 mL IA injection into the index glenohumeral joint under ultrasound guidance per the injection procedure.

---

#### **EFFICACY VARIABLES AND ENDPOINTS:**

The efficacy variables include the average daily shoulder pain with movement (NRS score); the Shoulder Pain and Disability Index (SPADI) pain subscale, disability subscale, and total score; the American Shoulder and Elbow Surgeons Standardized Shoulder Assessment Form (ASES) subscales for pain, function, and total; the Patient Global Impression of Change (PGIC) score; active and passive ROM; the EuroQol 5 Dimensions 5 Levels questionnaire (EQ-5D-5L); and responder status.

The primary efficacy endpoint for each of the shoulder conditions (glenohumeral OA and shoulder AC) in this study is the area under the curve (AUC) of the change from Baseline in the weekly mean of the average daily shoulder pain with movement score over 8 weeks for FX006 compared to placebo.

The secondary efficacy endpoints comparing FX006 to placebo for each of the shoulder conditions (glenohumeral OA and shoulder AC) in this study include the following:

- Change from Baseline in the weekly mean of the average daily shoulder pain with movement score at Week 12
- Change from Baseline in the SPADI pain subscale at Week 12
- Change from Baseline in the SPADI disability subscale at Week 12
- The PGIC score at Week 12
- Change from Baseline in the ROM of external rotation at Week 12

The exploratory efficacy endpoints comparing FX006 to placebo for each of the shoulder conditions (glenohumeral OA and shoulder AC) in this study include the following:

- AUC of change from Baseline in the weekly mean of the average daily shoulder pain with movement score over Weeks 4, 12, 16, 20, and 24
-

- 
- AUC of change from Baseline in the SPADI pain subscale over Weeks 4, 8, 12, 16, 20, and 24
  - AUC of change from Baseline in the SPADI disability subscale over Weeks 4, 8, 12, 16, 20, and 24
  - Change from Baseline in the weekly mean of the average daily shoulder pain with movement score at Weeks 1, 4, 8, 16, 20, and 24
  - Change from Baseline in the SPADI pain subscale at Weeks 1, 4, 8, 16, 20, and 24
  - Change from Baseline in the SPADI disability subscale at Weeks 1, 4, 8, 16, 20, and 24
  - Change from Baseline in the SPADI total score at Weeks 1, 4, 8, 12, 16, 20, and 24
  - The PGIC score at Weeks 1, 4, 8, 16, 20, and 24
  - Change from Baseline in the ROM of external and internal rotation, abduction and flexion at Weeks 4, 8, 16, 20, and 24
  - Change from Baseline in the ROM of internal rotation, abduction and flexion at Week 12
  - Change from Baseline in the ASES pain subscale at Weeks 1, 4, 8, 12, 16, 20, and 24
  - Change from Baseline in the ASES disability subscale at Weeks 1, 4, 8, 12, 16, 20, and 24
  - Change from Baseline in the ASES total score at Weeks 1, 4, 8, 12, 16, 20, and 24
  - Percent of responders based on the SPADI at Weeks 1, 4, 8, 12, 16, 20, and 24
  - Proportion of patients experiencing a  $\geq 20\%$ ,  $\geq 30\%$ , or  $\geq 50\%$  decrease in the weekly mean of the average daily shoulder pain with movement score at Weeks 1, 4, 8, 12, 16, 20, and 24
  - Change from Baseline in average weekly rescue medication use
  - Change from Baseline in the average weekly Sleep Interference score
  - Change from Baseline in the EQ-5D-5L at Weeks 1, 4, 8, 12, 16, 20, and 24
- 

#### **SAFETY VARIABLES:**

The safety variables include adverse events, physical examinations, index shoulder examinations, vital signs, and clinical laboratory evaluations.

---

#### **STATISTICAL ANALYSES:**

Data collected in this study will be presented using summary tables, figures, and patient data listings. Summary tables will present data by treatment group and, if applicable, by time of collection. Continuous variables will be summarized using descriptive statistics, specifically the mean, median, standard deviation, minimum, and maximum. Categorical variables will be summarized by frequencies and percentages. Figures will be used to support the presentation of certain data. Sensitivity analyses may be performed to examine the effect of missing data, as well as the effect of Baseline imbalance, should it occur.

All confidence intervals, statistical tests, and resulting p-values will be reported as 2-sided. Multiplicity will be addressed by analyzing the key secondary endpoints sequentially in the order presented in the protocol, testing each endpoint at the nominal  $\alpha = 0.05$ , 2-sided level to ensure

---

---

overall type I error control at the 2-sided 0.05 level. Each shoulder condition will be analyzed completely separately. In general, the same analysis methods will be used for both shoulder conditions.

For each shoulder condition, the following populations are planned for this study:

- Full Analysis Set (FAS) Population: All patients who receive a complete dose of study medication and have Baseline and at least 1 post-dose efficacy endpoint assessment. The FAS Population will be used to examine efficacy for both the primary and secondary endpoints.
- Safety Population: All patients who receive at least 1 dose of study medication. The Safety Population will be used to assess safety and tolerability.
- Per Protocol Population: All patients in the FAS Population who complete the Week 24 visit with no major protocol deviations that may impact the evaluation of the primary efficacy endpoint based on blinded data prior to database lock.

All study analyses will be completed using analysis data sets that are derived from the Study Data Tabulation Model and follow the Clinical Data Interchange Standards Consortium Analysis Data Model architecture.

Covariates for efficacy analyses will include Baseline average daily shoulder pain with movement score, Baseline score for the endpoint, analysis site, and, for AC patients, pain duration since onset. Other covariates may also be explored.

---

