### **6.3 Screening Visit (Days -21 to -1)**

The study will include a Screening Period of a maximum of 21 days. The following procedures will be performed at the Screening Visit:

- Obtain informed consent.
- Confirm eligibility based on Inclusion and Exclusion Criteria (see Sections 4.1 and 4.2, respectively).
- Complete APR and PRR trainings prior to patient questionnaires.
- Administer the PD-Q, PHQ-9, GAD-7, PCS, and ISI.
- Record medical history, including OA medical history and AC medical history.
  - For glenohumeral OA patients, OA medical history will include American College of Rheumatology diagnosis details; OA diagnosis date (if available); number of days with index shoulder pain in the last month; previous IA corticosteroid, PRP, or hyaluronic injections; presence of OA in other joints; and prior procedures or surgeries for index shoulder OA.
  - For AC patients, AC diagnosis date (if available); pain duration since onset at Screening; previous IA corticosteroid, PRP, or hyaluronic injections; presence of OA in other joints; and prior procedures or surgeries for index shoulder AC.
- Record patient demographics.
- Record prior treatments and medications.
- Record the average daily shoulder pain with movement score (0 to 10 NRS), SI question, and rescue medication usage in the eDiary.
- Record the pain with duration since onset (AC patients only).
- Perform physical examination.
- Perform shoulder assessment, including active and passive ROM, on the index and contralateral shoulder.

- Perform index shoulder X-ray.
  - X-ray of the index shoulder will include axillary view and true anterior-posterior view.
  - For glenohumeral OA patients, the Screening Visit X-ray will be read centrally to confirm Grade 2 or 3 OA in the index glenohumeral joint based on the Samilson-Prieto classification system.
  - For shoulder AC patients, the Screening Visit X-ray will be read centrally to confirm there is no evidence of OA in the index shoulder.
  - An x-ray acquired within 6 weeks of the Screening Visit may be used for study qualification if the specified imaging protocol was followed. The x-ray will be read centrally to confirm there is no evidence of OA in the index shoulder.
- Obtain vital signs.
- Perform ECG.
- Record height and weight and calculate BMI.
- Collect blood samples for hematology and chemistry, including hemoglobin A1c.
- Perform HIV, HBsAg, and HCV screens.

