#### **6.4 Treatment Visit (Day 1)**

The following procedures will be performed at the Treatment Visit (Day 1):

- Confirm eligibility based on Inclusion and Exclusion Criteria (see Sections 4.1 and 4.2, respectively) prior to administration of study medication.
  - Review the average daily shoulder pain with movement (0 to 10 NRS) to ensure at least 5 out of the 7 days prior to Day 1 have been recorded.
- Complete APR and PRR trainings prior to patient questionnaires and administration of study medication.
- Administer the EQ-5D-5L, SPADI, and ASES after completion of APR and PRR training, but prior to any other assessments.
- Review and update medical history prior to administration of study medication.

- Review and update prior treatments and medications prior to administration of study medication.
- Review SI question and rescue medication usage in the eDiary.
- Perform index shoulder assessment including active and passive ROM prior to administration of study medication.
- Obtain vital signs prior to administration of study medication.
- Perform urine pregnancy test prior to administration of study medication (for women of childbearing potential).
- Perform randomization prior to administration of study medication.
- Perform index shoulder aspiration prior to administration of study medication.
- Administer study medication following standard of care procedure.
- Dispense/return rescue medication as needed.
- Assess adverse events and concomitant medications (post injection).
- For shoulder AC patients only, a Home Exercise Program (HEP) will be implemented 3 days following injection and performed twice daily (see Appendix C).

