### **8.13 Index Shoulder Assessment**

The index shoulder assessment will be performed by the blinded assessor at the days indicated in Appendix A. The index shoulder will be assessed for tenderness, heat/redness, swelling, and effusion. The index shoulder assessment will also include a measurement of active and passive ROM. Ranges of motion will be measured with a goniometer and include glenohumeral joint flexion, glenohumeral joint abduction, glenohumeral external rotation, and glenohumeral internal rotation in 45° or comfort abduction as defined in Appendix D. Ranges of motion assessments will be performed bilaterally (on the index and contralateral shoulder) at the Screening Visit.

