#### 9.4.1.2 Secondary efficacy analyses

The key secondary change from Baseline endpoints will be analyzed with longitudinal mixed models for repeated measures with fixed effects for treatment group, study week, treatment-by-week interaction, analysis site, and Baseline score. Patient will be the random effect. Treatment differences from control will be estimated via LSMs from the analysis model along with 95% CIs and associated 2-sided p-values. This model assumes data are missing at random and includes only observed data. In addition, the model for shoulder AC will also include a covariate for pain duration since onset.

Multiplicity will be addressed by analyzing the key secondary endpoints sequentially in the order presented in the protocol, testing each endpoint at the nominal  $\alpha = 0.05$ , 2-sided level to ensure overall type I error control at the 2-sided 0.05 level.

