#### 9.4.5 Subgroups and Covariates

Preplanned subgroup analyses including aspiration status, OA grade based on the Samilson-Prieto classification system, gender, and Baseline average daily shoulder pain with movement score will be detailed in the SAP. In addition, subgroups of pain duration since onset are preplanned for shoulder AC patients. Further subgroups may be defined and explored after all preplanned analyses have been completed to further elucidate study results.

Covariates for efficacy analyses will include Baseline average daily shoulder pain with movement score, Baseline score for the endpoint, analysis site, and, for AC patients, pain duration since onset. Other covariates may be explored and will be fully defined in the SAP.

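### The external-rotation model names one pre-dose range-of-motion term although three relevant readings are collected; some precision, of uncertain size, goes unused

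*Combined protocol and SAP*

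**What the plan says.** **Endpoint.** The fifth and last secondary endpoint in the synopsis and Section 7.1.2 is "Change from Baseline in the ROM of external rotation at Week 12". Section 9.4.1.2 tests the key secondary endpoints in listed order, each at two-sided 0.05.

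**Model.** Section 9.4.1.2 specifies a repeated-measures model with "fixed effects for treatment group, study week, treatment-by-week interaction, analysis site, and Baseline score", plus pain duration since onset in AC. The synopsis and Section 9.4.5 give a longer list: "Covariates for efficacy analyses will include Baseline average daily shoulder pain with movement score, Baseline score for the endpoint, analysis site", again with pain duration in AC. Section 9.4.5 adds that "Other covariates may be explored and will be fully defined in the SAP".

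**Data already scheduled.** Section 6.3 (Screening): "Perform shoulder assessment, including active and passive ROM, on the index and contralateral shoulder". Section 8.13 repeats it: "Ranges of motion assessments will be performed bilaterally (on the index and contralateral shoulder) at the Screening Visit". Section 6.4 (Day 1): "Perform index shoulder assessment including active and passive ROM prior to administration of study medication".

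**Role of the other shoulder.** AC entry requires a loss of passive rotation arc "compared with the contralateral shoulder, and no X-ray evidence of OA". Section 4.2 excludes bilateral AC. It allows bilateral osteoarthritis (OA) unless contralateral OA pain exceeds 3.0.

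**The concern.** Three pre-randomisation readings bear on external rotation at Week 12: index shoulder at Screening, index shoulder on Day 1, and contralateral shoulder at Screening. The named model uses one value.

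The other two could carry information for different reasons. A second index reading dilutes goniometer error in the baseline covariate. The contralateral reading indicates the patient's own normal range: two patients with the same stiff index shoulder but different normal ranges have different room to improve. The protocol uses that comparison to define AC, but not to model recovery.

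What is at stake is precision. If the unused readings are prognostic, the confidence interval for this endpoint, and for every exploratory ROM comparison in Section 7.1.3, is wider than it needs to be at the same number of patients.

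**Working it through.** **1. The plan's own figure.** Section 9.4.6 sizes the study on Week 12 pain. By the normal approximation, power is Φ(δ / (SD·√(2/n)) − 1.96).
- OA, 68 per arm: 1 / (2·√(2/68)) = 2.916, giving 83.0%.
- AC, 57 per arm: 1.2 / (2.1·√(2/57)) = 3.051, giving 86.2%.

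The stated power above 80% reproduces. It concerns pain; no effect, SD or power is given for external rotation. Everything below rests on assumed inputs.

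**2. Second index reading alone.** Let r be the correlation of a pre-dose reading with Week 12, and r0 the correlation of Screening with Day 1. One reading leaves a residual share of 1 − r²; two leave 1 − 2r²/(1 + r0).

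| r | r0 | Two readings ÷ one | Equivalent extra patients |
|---|---|---|---|
| 0.5 | 0.9 | 0.7368 / 0.75 = 0.982 | 1.8% |
| 0.6 | 0.8 | 0.60 / 0.64 = 0.938 | 6.7% |
| 0.7 | 0.8 | 0.4556 / 0.51 = 0.893 | 12.0% |

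The gain is small when the two readings agree closely.

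**3. Adding the contralateral reading, by correlations.** Over r 0.5 to 0.7 and r0 0.8 to 0.9, the total gain in equivalent patients is 3.1% to 12.5% if contralateral ROM correlates 0.2 with both the index baseline and Week 12. It is 7.6% to 17.6% if the correlation with Week 12 is 0.3 instead.

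**4. Adding it, by a simulated recovery model for AC.** Assumed inputs:
- contralateral rotation: mean 65 degrees, SD 8 or 12
- index shoulder: on average 55% of it (SD 15%, cut at 80%)
- share of the deficit regained by Week 12: mean 30% or 50%, SD 20% or 40%
- measurement error SD: 4 or 7 degrees.

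This makes 16 settings. The reference model has Day 1 index ROM only; site, pain, pain duration and the repeated-measures structure are not simulated. Cut in residual variance:

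| Added to Day 1 index ROM | Gain proportional to deficit | Gain independent of deficit |
|---|---|---|
| Screening index ROM | about 1.5% to 9% | about 3% to 11% |
| Contralateral ROM | about 2.5% to 29% | about 0.2% to 2.4% |
| Both | about 5% to 31%, median about 12% | about 3% to 11 or 12% |

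The right-hand column keeps the same mean and SD of gain but cuts its link to the deficit. Only one of the 16 proportional settings exceeds 25% (contralateral SD 12, recovery 50% with SD 20%, error SD 4).

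**5. Conversion.** Equivalent extra patients are 1/(1 − cut) − 1. A 5% cut gives 5.3%, a 12% cut 13.6% and a 31% cut 44.9%. A comparison with 60% power moves to Φ((1.96 + 0.253)/√(1 − cut) − 1.96), which is about 62%, 66% and 76% respectively.

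**6. Price.** Two covariates inflate the variance of the treatment difference by roughly 2/N: 2/114 = 1.8% in AC and 2/136 = 1.5% in OA. If about 35 sites were fitted unpooled in AC, 2/(114 − 34) = 2.5%. At the bottom of the ranges the net gain is close to nil; at the medians it is clearly positive in the proportional case.

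**The case against.** - **The planned model is standard and valid.** This stands. Change adjusted for its own baseline, site and, in AC, pain duration is a sound analysis. A reader might infer that omitting the other readings biases the comparison; nothing in the documents supports that.
- **The SAP may already add the terms.** Section 9 defers to a SAP approved before database lock, and its text is not among the documents. It cannot be said that the terms will be absent. But permission to explore other covariates does not put them in the tested model.
- **It is not certain that only one reading is used.** This stands as a caution. Baseline for ROM is never defined as the Day 1 value, the last pre-dose value or a mean. One value is the natural reading, and the missing definition is itself a gap.
- **The contralateral gain is built into the recovery model.** This largely stands. A reader might take the upper end, about 45% more patients, as the information lost. That is one favourable setting of an unverified model, and without proportional recovery the contralateral term adds almost nothing.
- **The argument is weaker in OA.** This stands: the other shoulder may also be arthritic, and no OA figure was simulated.
- **The endpoint is last in sequence, in a Phase 2 study sized on pain.** This stands for confirmatory testing. The confidence interval is to be estimated in any case, and the gain extends to the exploratory ROM endpoints.

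**Conclusion.** The point holds as an inexpensive improvement in precision. The schedule yields two further pre-randomisation ROM readings that the named model does not use. Under assumed inputs for AC, using both cuts residual variance by about 5% to 31% (median about 12%) if recovery is proportional to the contralateral deficit, and by about 3% to 11 or 12% otherwise, before the small cost in degrees of freedom. Which case applies cannot be settled from the documents. The contralateral term is justified mainly in AC. The second index reading is justified in both conditions, modestly if Screening and Day 1 agree closely.

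Two specification gaps hold whatever the gain: Baseline ROM is undefined, and the endpoint is not identified as active or passive although both are measured. A reader might also assume that the covariate lists agree. They do not: Section 9.4.1.2 omits Baseline pain, which the synopsis and Section 9.4.5 include.

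**What to change.** Before unblinding, in Sections 9.4.1.2 and 9.4.5 and in the SAP, with the synopsis list aligned:

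1. Define Baseline ROM as the Day 1 pre-dose value.
2. State whether the external-rotation endpoint is active or passive.
3. For ROM endpoints, prespecify two further fixed covariates in the same plane and mode: Screening index ROM, and Screening contralateral ROM (at least in AC). Enter Screening index ROM as its own term rather than averaging it with Day 1, because medication washout falls between the two visits and the readings may not be exchangeable.
4. Reconcile Section 9.4.1.2 with the other two lists on whether Baseline pain is in the model.

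The cost is a few sentences and about two degrees of freedom per model. No new data, visits or patients are needed.
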